5.4.2.1. Binary Endpoints

All binary endpoints defined using HBsAg values/changes from baseline (HBsAg cut-offs, HBsAg seroclearance/seroconversion, Functional Cure) will be analyzed.

For single arm point and 90% CI estimates the Clopper Pearson method will be used. For the difference between paired matched case-control binomial proportions, the McNemar test at 0.05 one-sided Type 1 error rate will be used.

Graphical displays using bar charts will show the binary endpoints over time, by subgroups of interest, or combining multiple binary endpoints together.

5.4.2.1.1. LOCF Imputation Method

- If the lab value at FU Week 12 is missing, the LOCF in conjunction with the next available observation imputation approach will be used. The available non-missing lab test closest to FU Week 12 which is no earlier than FU Week 4 and no later than FU Week 24 will be imputed. If the non-missing lab value before and after the specific timepoint fall equidistant from the target timepoint, the later one will be used to impute the missing value.
- If the lab value at FU Week 24 is missing, the LOCF in conjunction with the next available observation imputation approach will be used. The available non-missing lab test closest to FU Week 24 which is no earlier/later than 12 weeks from the actual time point of interest (FU Week 12 and FU Week 36, respectively) will be imputed.
- If the lab value at FU Week 36 is missing, the LOCF in conjunction with the next available observation imputation approach will be used. The available non-missing lab test closest to FU Week 36 which is no earlier/later than 12 weeks from the actual time point of interest (FU Week 24 and FU Week 48, respectively) will be imputed.
- If the lab value at FU Week 48 is missing, the LOCF approach will be used with the condition that no value earlier than FU Week 36 may be carried forward.

5.4.2.1.2. NA Treatment Completion Criteria at Week 24 and During FU

The count and proportion of participants (and associated 90% CI) who met the NA treatment completion criteria at the end of treatment period 2, will be summarized.

Starting at end of treatment period 2, the incidence of participants who did not meet the NA treatment completion criteria will be summarized at each timepoint during the study, accompanied by the distribution of each of the 4 criteria that is not met. The NA treatment completion criteria are based on a threshold for the laboratory tests of ALT, HBV DNA, HBeAg and HBsAg.

The count and proportion of participants (and associated 90% confidence interval) who met the NA treatment completion criteria (Section 5.4.1.1.1) at any time during the FU phase will be summarized. All the NA treatment completion criteria will be checked based on clinical laboratory tests in FU phase.

5.4.2.1.2.1. NA Re-Treatment Criteria During FU

The count and proportion of participants (and associated 90% CI) who meet the criteria for NA re-treatment at any time during FU will be summarized descriptively. In addition, the count and proportion of participants (and associated 90% CI) who met the criteria according to the flag on the CRF page of 'NA Re-treatment Criteria Assessment' during the follow-up phase will be summarized over time.

The count and proportion of participants (and associated 90% CI) who re-started NA treatment during the follow-up phase on the basis of the ‘Study Drug Administration for NA’ CRF page will be summarized separately over time.

A cross-tabulation of participants who actually re-started NA treatment (re-started/not restarted) versus participants who met the above criteria (met/not met) will be presented over time.

5.4.2.1.2.2. HBsAg Cut-offs

The cut-offs for HBsAg values, decreases from baseline and RT will be used in separate summaries over time. The count and proportion of participants who meet those HBsAg thresholds during the study will be summarized descriptively by analysis phase over time and displayed in graphs like bar charts.

Cross-tabulations overtime of quantitative HBsAg (<LLOQ, ≥LLOQ) versus qualitative HBsAg (positive, negative), respectively, will also be presented.

5.4.2.1.3. HBsAg Seroclearance

5.4.2.1.3.1. On Treatment

The count and proportion of participants (and associated 90% CI) who achieve HBsAg seroclearance over time during the study intervention phase will be summarized.

5.4.2.1.3.2. Off Treatment

The count and proportion of participants (and associated 90% CI) who achieve HBsAg seroclearance over time during FU will be summarized. Separate analyses will be performed for participants who completed treatment as planned (at the end of treatment period 2), and regardless when treatment was stopped.

The count and proportion of participants who achieve HBsAg seroclearance will be evaluated at each of the following off-treatment time points: 12, 24, 36 and 48 weeks, respectively, after stopping all study interventions and without restarting NA treatment. In an additional summary, these proportions will be calculated with the denominator including only those participants who have reached the off-treatment timepoint (week 12, 24, 36 or 48), and have stopped all interventions including NA and have not restarted NA prior to the timepoint of interest.

For all time points, HBsAg seroclearance will be analyzed using the observed case data. LOCF will be used for selected time points (Section 5.4.2.1.1).

5.4.2.1.4. Functional Cure

The count and proportion of participants (and associated 90% CI) who achieve FC at each of the selected FU time points will be summarized descriptively.

The main analysis will be on observed cases data with no imputation of missing values.

Two sensitivity analyses will be performed.

1. Missing as non-response: If participants withdrew from the study prior to the selected FU time point or had missing HBsAg values at the selected FU time point, they will be considered as non-responders.
2. LOCF: If participants withdrew from the study prior to the selected FU time point, they will be considered as non-responders. The LOCF rules to handle missing data will be applied to selected time points as explained in Section 5.4.2.1.1.

5.4.2.1.5. Treatment Failure

The count and proportion of on-treatment failure participants (and associated 90% CI) will be summarized.

5.4.2.1.6. HBsAg Seroconversion

The count and proportion of participants (and associated 90% CI) who achieve HBsAg seroconversion will be summarized descriptively by analysis phase.

For participants achieving HBsAg seroconversion, descriptive statistics will be calculated for the level of anti-HBs antibodies at the timepoint when achieving the HBsAg seroconversion. In an additional summary, the level of anti-HBs antibodies at the specific timepoint will be summarized for the subset of the participants achieving HBsAg seroconversion at any time before or at that given timepoint.

In addition, the count and proportion of participants (and associated 90% CI) with appearance of anti-HBs antibodies but without seroclearance of HBsAg will also be summarized by analysis phase.

5.4.2.1.7. HBeAg Cut-offs

The cut-offs for HBeAg values, decreases from baseline and RT will be used in separate summaries over time. The count and proportion of participants who meet those HBeAg thresholds during the study will be summarized descriptively by analysis phase over time and displayed in graphs like bar charts.

Cross-tabulations overtime of quantitative HBeAg ($<LLOQ$, $\geq LLOQ$) versus qualitative HBeAg (positive, negative), respectively, will also be presented.

5.4.2.1.8. HBeAg Seroconversion

The count and proportion of participants (and associated 90% CI) who achieve HBeAg seroconversion will be summarized by analysis phase. Separate tabulations will be made for the subset of participants who were HBeAg positive at baseline and for the subset of participants who were anti-HBe negative at baseline, respectively. The seroconversion will only be assessed at the time points when the anti-HBe antibodies assessment is available.

In addition, the count and proportion of participants (and associated 90% CI) with HBeAg seroclearance and without appearance of anti-HBe antibodies will also be summarized by analysis phase.

5.4.2.1.9. HBV DNA Cut-offs

The cut-offs for HBV DNA values will be used in separate summaries over time. The count and proportion of participants who meet those HBV DNA thresholds during the study will be summarized descriptively by analysis phase over time.

5.4.2.1.10. Suppressed HBV DNA

The count and proportion of participants (and associated 90% CI) with HBV DNA <LLOQ (overall and separately for HBV DNA detectable and HBV DNA TND) will be evaluated by analysis phase over time.

The count and proportion of participants (and associated 90% CI) with HBV DNA <LLOQ (overall and separately for HBV DNA detectable and HBV DNA TND) will be evaluated at each of the FU Weeks 12, 24, 36, and 48, respectively, after stopping all study interventions at the end of treatment period 2 and without restarting NA treatment.

The count and proportion of participants (and associated 90% CI) with HBV DNA <LLOQ (overall and separately for HBV DNA detectable and HBV DNA TND) will be evaluated at each of the following off-treatment timepoints: 12, 24, 36, and 48 weeks, respectively, after stopping all study interventions and without restarting NA treatment. In an additional summary, these proportions will be calculated with the denominator including only those participants who have reached the off-treatment timepoint (week 12, 24, 36 or 48), and have stopped all interventions including NA and have not restarted NA prior to the timepoint of interest.

The count and proportion of participants (and associated 90% CI) with HBV DNA <LLOQ (overall and separately for HBV DNA detectable and HBV DNA TND) after restart of NA treatment during follow-up will also be presented.

The number of occurrences each subject has HBV DNA <LLOQ (overall and separately for HBV DNA detectable and HBV DNA TND) will be determined and summarized using frequency distributions and descriptive statistics. Additionally, the number of occurrences will be displayed graphically. For all time points, HBV DNA <LLOQ will be analyzed using the observed case data. LOCF will be used for selected time points (Section 5.4.2.1.1), if there is at least 10% of the participants with missing HBV DNA results for the selected time points.

5.4.2.1.11. Thresholds on HBV DNA and HBsAg

The number and proportion of participants who meet the following HBV DNA reduction and seroclearance thresholds at last available timepoint will be summarized descriptively. Only participants who stopped all study treatments without restarting NA will be assessed.

Thresholds based on HBV DNA and HBsAg

- HBV DNA < 2000 IU/mL
- HBV DNA < LLOQ
- HBsAg<LLOQ and HBV DNA<LLOQ

- HBsAg<100 IU/mL and HBV DNA<LLOQ
- HBsAg<100 IU/mL and HBV DNA<2,000 IU/mL

5.4.2.1.12. ALT Normalization

The count and proportion of participants (and associated 90% CI) who achieve ALT normalization on treatment and off treatment but without restarting NA treatment will be summarized descriptively over time, only for the subjects who had ALT elevation ($ALT \geq ULN$) at baseline.

The count and proportion of participants (and associated 90% CI) who have $ALT \geq ULN$ before NA re-treatment and reach ALT normalization after NA re-treatment during follow-up will be summarized.

5.4.2.1.13. Partial Cure

The count and proportion of participants (and associated 90% CI) who achieve partial cure during the study will be summarized descriptively at the selected FU time points.

The main analysis will be on observed cases data with no imputation of missing values.

Two sensitivity analyses will be performed.

1. Missing as non-response: If participants withdrew from the study prior to the selected FU time point or had missing HBsAg or HBV DNA values at the selected FU time point, they will be considered as non-responders.
2. LOCF: If participants withdrew from the study prior to the selected FU time point, they will be considered as non-responders. The LOCF rules to handle missing data for HBsAg and HBV DNA will be applied to selected time points as explained in Section [5.4.2.1.1](#).

5.4.2.1.14. Virologic Breakthrough

The count and proportion of participants (and associated 90% CI) who experience a virologic breakthrough and those who experience virologic breakthrough followed by on-treatment biochemical flare will be summarized, respectively, by analysis phase.

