1.1. Objectives and Endpoints

Objectives	Endpoints
Primary	

 To evaluate the efficacy in terms of HBsAg levels of the study intervention (i.e. JNJ-3989 + JNJ-6379^d + NA and PegIFN-α2a). 	
 Proportion of participants with a reduction of at least 2 log₁₀ IU/mL in HBsAg levels from baseline to Week 24 (end of study intervention [EOSI]).
Secondary	

 To evaluate the safety and tolerability of the study intervention. 	
 Safety and tolerability including but not limited to the proportion of participants with (serious) adverse events (S)AEs and abnormalities in clinical laboratory tests (including hematology, blood biochemistry, blood coagulation, urinalysis, urine chemistry, and renal biomarkers), 12-lead electrocardiograms (ECGs), vital signs, and ophthalmic and physical examinations throughout the study.

 To evaluate the efficacy of the study intervention at the end of the 24-week treatment period. 	
 Proportion of participants meeting the protocol-defined NA treatment completion criteria at EOSI.

 To evaluate the efficacy of the study intervention as measured by blood markers (such as HBsAg, HBeAg^a, HBV DNA, and alanine aminotransferase [ALT]) during the study intervention and follow-up (FU) period. 	
 Proportion of participants with HBeAg^a, HBsAg, HBV DNA, and ALT levels below/above different cut-offs. Proportion of participants with HBsAg and/or HBeAg^a seroconversion.

Objectives	Endpoints
	
 Change from baseline over time in HBsAg, HBeAg^a, and/or HBV DNA. Time to achieve HBsAg and/or HBeAg^a seroclearance/seroconversion, and/or HBV DNA < lower limit of quantification (LLOQ).

 To evaluate the frequency of virologic breakthrough^b during the 24-week treatment period, as well as during the FU period for participants who continue treatment with NA. 	
 Proportion of participants with virologic breakthrough^b.

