1.2. Study Design

This is a Phase 2a, open-label, single-arm, multicenter study to assess efficacy, safety, tolerability and pharmacokinetics of treatment with JNJ-3989, JNJ-6379 (as applicable), NA, and PegIFN- α 2a in virologically suppressed patients with chronic hepatitis B virus infection. Prior to Protocol Amendment 3, the study intervention also included JNJ-6379. Note that as of Protocol Amendment 3, JNJ-6379 has been removed as study intervention and the study will continue with JNJ-3989, NA and PegIFN- α 2a only. Participants had to stop JNJ-6379 treatment immediately after the implementation of Urgent Safety Measure (USM) and approval of the protocol amendment 3.

Approximately 50 virologically suppressed CHB-infected participants, 18-65 years (inclusive) of age, will be enrolled in this study. Approximately 40% HBeAg-positive participants will be enrolled.

[figure not shown]
The study will be conducted in 4 periods:

- Screening period (4 weeks [if necessary, can be extended to a maximum of 8 weeks decided on a case-by-case basis and in agreement with the sponsor]).
- Treatment Period 1 (12 weeks) consisting of combination treatment with JNJ-3989 + NA.
- Treatment Period 2 (12 weeks) adding PegIFN- α 2a to the combination treatment regimen of Treatment Period 1.
- Follow-up (FU) Period (48 weeks).

The total duration of individual participation will be up to 76 weeks (including 4 weeks of screening).

A schematic of the trial prior to Protocol Amendment 3 is presented in [Figure 1](#).

Figure 1: Schematic Overview of the Study – Prior to Protocol Amendment 3

[figure not shown]

ALT: alanine aminotransferase; DNA: deoxyribonucleic acid; EOS: end of study; EOSI: end of study intervention; FU: follow-up; HBeAg: hepatitis B e antigen; HBsAg: hepatitis B surface antigen; HBV: hepatitis B virus; JNJ-3989: JNJ-73763989; JNJ-6379: JNJ-56136379; LLOQ: lower limit of quantification; n: number of participants; NA: nucleos(t)ide analog; PegIFN-α2a: pegylated interferon alpha-2a; ULN: upper limit of normal; Q4W: every 4 weeks; QD: once daily; QW: once weekly.

^a. If NA treatment completion criteria (HBsAg <10 IU/mL, and HBeAg-negative, and HBV DNA <LLOQ, and ALT <3x ULN) have been met at Week 24, NA will be stopped at the next scheduled visit (ie, FU Week 2), otherwise NA treatment will continue during the complete FU period.

A schematic of the trial as of Protocol Amendment 3 is presented in [Figure 2](#).

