4. POPULATIONS (ANALYSIS SETS) FOR ANALYSIS

Due to a potential impact of future Coronavirus Disease (COVID-19) pandemics on the study data collection, study treatment adherence and study conduct, the modified Full Analysis Set (mFAS) and modified IFN-FAS (mIFN-FAS) are defined to target the estimation of effects without the pandemic-related influences.

The primary set for the efficacy analyses will be the FAS set, and for the safety analyses the safety set. The IFN-FAS and modified FAS/IFN-FAS analysis sets will be used if there is a difference of at least 2 participants between analysis sets.

Table 2: Analysis Sets for Analysis

Analysis Sets	Description
Screened	All participants who signed the ICF for the Master Protocol and an ICF specific for the ISA.
Enrolled	All participants who were enrolled in this ISA.
Full Analysis Set (FAS)	All participants who were enrolled and who received at least 1 dose of study intervention within this ISA.
Modified FAS	All participants who were enrolled and who received at least 1 dose of study intervention excluding those participants who, because of COVID-19 or similar pandemics related reasons, withdrew prematurely from the study prior to Week 24 (end of study intervention [EOSI]), or had no efficacy assessment for the primary endpoint. COVID-19 or similar pandemics related reasons may include for example missed visits due to travel restriction, shortage of lab kits at the planned visit, missed collection of blood sample at key time points for the primary efficacy endpoint, etc.
IFN-FAS	All participants who were enrolled and who received at least 1 dose of PegIFN- α 2a within this ISA.
Modified IFN-FAS	All participants who were enrolled and who received at least 1 dose of PegIFN- α 2a excluding those participants who, because of COVID-19 or similar pandemics related reasons, withdrew prematurely from the study prior to Week 24 (EOSI), or had no efficacy assessment for the primary endpoint. COVID-19 or similar pandemics related reasons may include for example missed visits due to travel restriction, shortage of lab kits at the planned visit, missed collection of blood sample at key time points for the primary efficacy endpoint, etc.
Safety	All participants who received at least 1 dose of study intervention. Participants will be analyzed according to the study intervention they actually received.

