5.4.1.1.15. Virologic Breakthrough

HBV virological breakthrough is defined as having a confirmed on-treatment HBV DNA increase by $>1 \log_{10}$ from nadir level (lowest level reached during treatment) in participants who didn't have on-treatment HBV DNA level below the lower limit of quantification (LLOQ) or a confirmed on-treatment HBV DNA level >200 IU/mL in participants who had on-treatment HBV DNA level below the lower limit of quantification (LLOQ). Confirmed HBV DNA increase/level means that the criterion should be fulfilled at 2 or more consecutive time points or at the last observed on-treatment time point. On-treatment will be defined as the time period in which the participant receives any of the study interventions (including NA).

In addition, participants who experience a virologic breakthrough followed by on-treatment biochemical flare will be evaluated.

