5.4.2. Analysis Methods

All secondary endpoints will be analyzed using the FAS. The analysis may be repeated in the IFN-FAS and modified FAS/IFN-FAS analysis sets if there is a difference of at least 2 participants between analysis sets.

Some analysis will be performed by group, as defined in Section 5.1.10. Summaries and graphs will be provided for each analysis phase, unless specified otherwise.

All secondary endpoints will be analyzed based on the observed case data. Additional analyses with specific imputation methods for missing data are added for selected endpoints.

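### The follow-up virologic breakthrough rate is set on the FAS, although its objective covers only participants who continue NA

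*SAP*

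**What the plan says.** The secondary objective (SAP 1.1; same wording in protocol Section 3 and the synopsis) covers breakthrough during the 24-week treatment period, "as well as during the FU period for participants who continue treatment with NA". The paired endpoint is simply the proportion with breakthrough.

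The analysis rules are general. SAP 5.4.2: "All secondary endpoints will be analyzed using the FAS". The FAS (SAP Section 4) is "All participants who were enrolled and who received at least 1 dose of study intervention within this ISA", with no condition on NA status in follow-up. SAP 5.4.2 also sets the missing-data rule: "All secondary endpoints will be analyzed based on the observed case data". For this endpoint, SAP 5.4.2.1.14 says that the count, proportion and 90% CI of participants "who experience a virologic breakthrough and those who experience virologic breakthrough followed by on-treatment biochemical flare will be summarized", separately for each analysis phase. It names no denominator for the follow-up phase.

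The event itself is limited to time on treatment (SAP 5.4.1.1.15): "On-treatment will be defined as the time period in which the participant receives any of the study interventions (including NA"). For participants who meet the completion criteria at Week 24, SAP 1.2 says: "NA will be stopped at the next scheduled visit (ie, FU Week 2), otherwise NA treatment will continue during the complete FU period". SAP 5.1.11 ends the off-treatment period when NA re-treatment begins. SAP Appendix 2 declares no changes to the protocol-planned analyses.

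**The concern.** The numerator and the denominator follow different rules. An event needs the participant to be on study intervention; membership of the denominator does not. A participant who stops NA at FU Week 2 spends nearly all of a 48-week phase outside the event definition, and is still counted as free of breakthrough.

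At stake is whether this secondary endpoint answers its stated question: how often HBV DNA breaks through in people kept on NA after the other agents stop. Under the rules as written, the reported rate also depends on how many participants stop NA. Two cohorts with the same breakthrough rate on NA would show different figures if different numbers met the stopping criteria.

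**Working it through.** **The plan's own figures.** The documents give no planning figure for breakthrough, so the check starts with the interval method. Exact Clopper-Pearson 90% limits for 25 of 50 are 0.376 to 0.624 (width 0.248), as in SAP Table 1. All eight intervals in that table reproduce to three decimals.

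**Inputs.** N = 50 is the planned enrolment (SAP 1.2). The number who stop NA, s, and the number of breakthroughs, x, are not planned anywhere; the share meeting the completion criteria is itself an endpoint. Both are assumptions below.

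**Time at risk for those who stop.** FU Week 2 is FU day 15 and FU Week 48 is FU day 337 (SAP Table 4). With the two days after the last NA dose allowed in SAP 5.1.11, a participant who stops is on treatment for about 17/337 = 5.0% of follow-up.

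**Does the observed-case rule remove them?** No. The Schedule of Activities samples HBV DNA at FU Week 2 and at every later follow-up visit. Some later visits are optional only for participants continuing or restarted on NA. Those who stop therefore have data and remain observed cases.

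**Dilution when nobody restarts.** With all x events among the N−s continuers, the reported rate is x/N and the target is x/(N−s). Their ratio is (N−s)/N.

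| s (assumed) | Continuers | Ratio | 3 events: FAS | 3 events: continuers |
|---|---|---|---|---|
| 0 | 50 | 1.00 | 6.0% | 6.0% |
| 5 | 45 | 0.90 | 6.0% | 6.7% |
| 10 | 40 | 0.80 | 6.0% | 7.5% |
| 20 | 30 | 0.60 | 6.0% | 10.0% |
| 25 | 25 | 0.50 | 6.0% | 12.0% |

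With no events the point estimate is 0% either way, and the upper 90% limit is 1 − 0.05^(1/n): 5.8% for n = 50, 7.2% for n = 40, 9.5% for n = 30.

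**The opposite direction.** A participant who stops NA, rebounds and restarts is again receiving study intervention. Meeting the completion criteria required HBV DNA below LLOQ at Week 24, so the 200 IU/mL breakthrough threshold applies. The HBV DNA restart triggers in protocol 6.7.1 begin at 2,000 IU/mL, ten times that level, so values just after restart could qualify as breakthrough. If r such participants are counted, the reported rate is (x+r)/N, which exceeds x/(N−s) when r > x·s/(N−s). For s = 20 and x = 1, the bound is 20/30 = 0.67, so one restarter is enough: the continuers' rate is 1/30 = 3.3%, against a reported 2.0% (r = 0), 4.0% (r = 1), 6.0% (r = 2) or 12.0% (r = 5).

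**Comparison within the SAP.** Sections 5.4.2.1.3.2 and 5.4.2.1.10 add summaries with a denominator limited to participants off all treatment who have not restarted NA. Section 5.4.2.1.11 limits its population in a similar way. Section 5.4.1.1.16 assesses virologic flare, the off-treatment counterpart of breakthrough, only in off-treatment participants and gives it a not-applicable code. Breakthrough has neither device.

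**The case against.** The strongest reply is that the SAP leaves the denominator unstated rather than choosing a wrong one. Section 5.4.2.1.14 names no denominator; the FAS comes from a general sentence, and with observed cases it would mean FAS participants with follow-up data, not necessarily all 50. The NA clause in the objective can be read as saying when breakthrough can occur in follow-up, and the on-treatment definition already applies that to the numerator. Off-treatment rises have their own endpoint. Counts are reported beside proportions, and the number meeting the completion criteria is reported too, so a reader could approximate the restricted rate. Nothing formal depends on it: the study has no hypothesis and no test for this endpoint.

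Much of this stands, and it limits the consequence. It does not remove the mismatch. Followed as written, the general FAS rule, the on-treatment definition and the by-phase summary keep participants who stopped NA in the denominator, and the observed-case rule does not take them out.

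Two stronger readings are tempting. A reader might infer that the rate must be understated; restarters can reverse the direction, so the documents do not support that. A reader might also infer a large bias, such as a halved rate. That needs 25 of 50 to stop NA and some breakthroughs to occur, and neither is planned. The nearest rate in the protocol (2.2.3.1) is the JADE interim result, with no breakthroughs in the arms combining JNJ-6379 or placebo with NA. The investigational regimen differs and the data are from Week 24, but they give no support for several events.

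**Conclusion.** The point holds as a mismatch between objective and analysis population. The follow-up proportion, as specified, does not estimate breakthrough among participants who continue NA. Dilution by (N−s)/N is the usual direction, assuming that those who stop have no events and never restart; inflation is possible if restarters are counted. The size cannot be determined from the documents and is zero if nobody stops NA. The calculated rates are illustrations under assumed s, x and r, not forecasts. The treatment-period summary and the primary analysis are unaffected. It is worth correcting because it is inexpensive and because programmers who handle restarters differently could produce different tables.

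**What to change.** Add to SAP 5.4.2.1.14:

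*For the follow-up phase, the denominator is FAS participants who did not stop NA at or before FU Week 2 (i.e. continued NA in follow-up per the Study Drug Administration for NA CRF page) and who have at least one on-NA HBV DNA value in follow-up. Participants who stopped NA and later restarted are excluded from this proportion and reported separately.*

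Keep the FAS for the 24-week treatment period.

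The FU Week 2 cut is needed. A shorter condition, such as having continued NA beyond Week 24 with one on-NA value in follow-up, would readmit those who stop: they remain on NA until FU Week 2 and are sampled for HBV DNA at that visit.

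The cost is two sentences, a separate line for restarters and a smaller denominator with a somewhat wider interval. For 3 events, the 90% CI goes from 1.7–14.8% on 50 to 2.1–18.3% on 40. No new data are needed, since SAP 5.4.1.1.2 already uses that CRF page to identify NA restarts.
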